12.2.3. Vital Signs

Vital signs will be assessed at indicated visits: height, weight, temperature, sitting heart rate, respiratory rate, and sitting blood pressure. When taking heart rate, respiratory rate, and blood pressure readings, subjects should be seated quietly for a minimum of 3 minutes before the readings are taken.

12.2.4. Electrocardiogram

Standard 12-lead ECGs will be collected at the Screening Visit 1, Month 12, and at EOT/EOS. The Investigator or designee will review the 12-lead ECG and findings will be recorded in the CRF as normal, abnormal but not clinically significant, or abnormal and clinically significant. Any clinically significant abnormality on ECGs should be reported on the AE CRF page.

Investigative sites must retain a copy of all 12-lead ECGs evaluated by the Investigator or designee. These ECGs must be clearly labeled with the subject's initials, Subject ID number, date, and time.

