- ^r Urine β -hCG pregnancy tests must be performed in females of childbearing potential prior to entry. If positive, a confirmatory blood test must be performed at the central laboratory. If the blood test is also positive, the subject may not be enrolled in the study. (Additional testing may be conducted where required, regionally).
- ^s Only OCA PK samples will be collected at Month 9 at select study sites in a subset of subjects. Please refer to [Section 9.7.13](#) for the PK sampling schedule.
- ^t Markers of hepatic fibrosis and/or inflammation are defined in [Section 11.1.2](#).
- ^u A genetics study will be conducted in a subset of subjects who provide consent for analyses of these samples. Genetics samples will be collected at Day 0 and every other year beginning at Month 12.
- ^v Please refer to [Section 11.1.2.3](#) for description of the blood sample to be collected for future analysis.

Table 2: Schedule of Study Procedures – Year 2 Through End of Study (Table 2 of 2)

	Year 2 through End of Study					
	M 3 continued follow-up	1-Month Post- Titration Visit ^a (if applicable)	M 6 continued follow-up	M 9 continued follow-up	M 12 continued follow-up	EOT/ EOS ^b
Visit Windows (+/-)^c	±2 wk	+1 wk	±2 wk	±2 wk	±2 wk	±2 wk
Physical Exam ^d					X	X
Assessment for Mayo Risk Score ^e			X		X	X
Assessments for Child-Pugh Scores ^f	X		X	X	X	X
Vital Signs (including weight)			X		X ^g	X ^g
12-Lead Electrocardiogram					X	X
Subject Questionnaires (5-D Pruritus Scale and Pruritus VAS)			X		X	X
Quality of Life Questionnaires (PBC-40, EQ-5D-5L, and FIS) ^h					X	X
TE Fibroscan [®] /DEXA ⁱ					X	X
Endoscopy ^j					X	
Hepatic Ultrasound ^k					X	X
Adverse Events	X	X	X	X	X	X
Prior and Concomitant Medications	X	X	X	X	X	X
Health Outcome Assessments ^l	X		X	X	X	X
Dose Titration (if applicable) ^{m,n}	X		X	X	X	
Dispense Investigational Product	X		X	X	X	
IP Accountability/Compliance	X	X	X	X	X	X
Dosing Diary	X	X	X	X	X	X
LABORATORY EVALUATIONS^o						
Urinalysis					X	X
Chemistry/Hematology/Coagulation	X	X	X	X	X	X
OCA, C4, and FGF-19 (plasma)					X	X
Markers of Hepatic Fibrosis and/or Inflammation ^p			X		X	X

Table 2: Schedule of Study Procedures – Year 2 Through End of Study (Table 2 of 2) (Continued)

	Year 2 through End of Study					
	M 3 continued follow-up	1-Month Post- Titration Visit ^a (if applicable)	M 6 continued follow-up	M 9 continued follow-up	M 12 continued follow-up	EOT/ EOS ^b
Visit Windows (+/-) ^c	±2 wk	+1 wk	±2 wk	±2 wk	±2 wk	±2 wk
Genetics ^q					X	

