9.7.17. Month 12 Continued Follow-up Procedures (Annually [±2 weeks])

- Perform a physical examination (including smoking and alcohol consumption habits).
- Perform assessment for calculation of Mayo Risk Score.
- Perform assessments for calculation of Child-Pugh Score.
- Assess and record vital signs (height, weight, temperature, sitting heart rate, respiratory rate, and sitting blood pressure).
- Perform a standard 12-lead electrocardiogram (ECG).
- Quality of Life and Subject questionnaires (see [Section 11.1.2.2](#) and [Section 12.2.6](#)).
- Perform TE (at selected study sites, where available) using the Fibroscan[®] TE device.
- Conduct a DEXA bone density scan (selected study sites); document whether the subject stopped taking her/his calcium supplements for 48 hours before the scan and medications for osteoporosis or osteopenia on the day of the scan, if applicable.

- Perform an endoscopy (at selected study sites, where available) to assess the presence or absence of oesophageal varix/varices.
- Perform an ultrasound for HCC surveillance (if equipment is unavailable, sites should make every attempt to use available community referral sites).
- Assess and record AEs.
- Review and record concomitant medications.
- Review and record any non-study related medical or surgical treatment procedures and any medically relevant HCP or non-HCP related office visits that have occurred since the previous study visit.
- Assess for dose titration, if eligible (refer to [Section 7.4](#)).
- Assess investigational product compliance, perform accountability, and review dosing diary with the subject.
- Assess the subject's supply of investigational product to ensure an adequate amount. Access the IWRS and dispense investigational product.
- Verify that the subject has fasted for at least 8 hours.
 - Record fasting status in the source and CRF.
 - If the subject reports having eaten within 8 hours, document accordingly in the source and CRF and remind the subject that fasting is required prior to all study visits.
- Obtain urine sample for urinalysis.
- Obtain blood samples for serum chemistry, hematology, and coagulation tests.
- Obtain blood samples for:
 - OCA, C4, and FGF-19
 - Markers of hepatic fibrosis and/or inflammation (including ELF)
 - Genetics (see [Section 11.1.2.3](#))
 - Blood sample for future analysis (refer to [Section 11.1.2.3](#))
- Provide the subject with a dosing diary to document his or her dosing.

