13.2.3. Additional Safety Analysis

Additional safety assessments include vital signs and ECGs. Descriptive statistics of the vital sign and ECG parameters will be presented by treatment group and study visit, as well as the change from pretreatment at each visit.

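### ECGs are to be recorded as a three-level judgement, which cannot supply the ECG parameter statistics planned in 13.2.3; separately, the visit list in 12.2.4 does not match the annual schedule

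*Protocol*

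**What the plan says.** The point concerns the current protocol text (Version 3, dated 07 September 2016).

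- **Recording (12.2.4).** After review by the investigator or a designee, "findings will be recorded in the CRF as normal, abnormal but not clinically significant, or abnormal and clinically significant". No heart rate, PR, QRS, QT or corrected QT value is named. For the tracings themselves, "Investigative sites must retain a copy of all 12-lead ECGs evaluated by the Investigator or designee".
- **Timing (12.2.4).** "Standard 12-lead ECGs will be collected at the Screening Visit 1, Month 12, and at EOT/EOS".
- **Timing elsewhere.** Table 1 marks the ECG at Screening Visit 1 and Month 12. In Table 2, which runs from Year 2 to the end of the study, the row "12-Lead Electrocardiogram" is marked at the yearly continued follow-up visit and at EOT/EOS. Section 9.7.17, whose heading says that the visit is annual, also lists a 12-lead ECG.
- **Analysis (13.2.3).** "Descriptive statistics of the vital sign and ECG parameters will be presented by treatment group and study visit". The sentence goes on to promise a second summary, relative to the value before treatment: "as well as the change from pretreatment at each visit". The synopsis also lists the electrocardiogram among the safety data on which OCA and placebo are to be compared.

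**The concern.** Section 13.2.3 treats the ECG as a set of measurements. Section 12.2.4 records it as a single overall judgement. If the CRF follows 12.2.4, the ECG half of the sentence in 13.2.3 has no values to work on.

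What would be lost is a view of small, systematic changes in conduction or repolarisation. Suppose OCA lengthened an interval modestly in many subjects, and each investigator graded the tracing as not clinically significant. The categories could then look alike in the two arms although the group means had moved. Follow-up is long (a minimum of about 6 years), and the protocol takes cardiovascular safety seriously enough to adjudicate MACE. An ECG comparison that cannot be run as written is therefore worth repairing.

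The visit list is a second and independent inconsistency. It affects how many ECGs a reader of 12.2.4 expects, not whether parameter statistics can be formed.

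**Working it through.** There is no figure in the plan to reproduce. The check sets the sections side by side and then counts visits.

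**1. What the recorded variable allows.** Under 12.2.4 the variable at each visit is one of three levels. Change from pretreatment is Y(visit) − Y(Screening), which needs a numeric Y. The categories permit counts and percentages by visit and a 3 × 3 shift table from Screening. They do not permit a mean, a standard deviation or a numeric change.

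**2. Whether another section supplies the numbers.** The current sections shown describe no ECG interval field, no central reading and no transfer of measurements to the database. Section 14.1 lists ECGs among source documents that support CRF entries, but does not say which entries. Vital signs make a useful contrast: 12.2.3 names each one (weight, temperature, sitting heart rate, respiratory rate, sitting blood pressure and so on). The same sentence of 13.2.3 can therefore be carried out for vital signs.

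**3. Which measures are affected.** Sitting heart rate is a numeric vital sign. It is scheduled at Screening, Day 0 and Months 3, 6, 9 and 12, then at the semi-annual and annual visits and EOT/EOS. A drift in heart rate would be seen there. The gap is confined to PR, QRS and QT/QTc.

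**4. Counting ECGs between Screening and EOT/EOS.** Let T be years of follow-up. Section 7.1.3 gives a minimum of about 6 years and a total duration of about 8, so T runs from 6 to 8.

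- Section 12.2.4, read literally: Month 12 only, so 1 for every T.
- Tables 1 and 2: Month 12 plus one per year from year 2. If EOT/EOS takes the place of the last annual visit, the count is 1 + (T − 2) = T − 1. If EOT/EOS is separate, it is T.

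| T (years) | 12.2.4 | Tables 1 and 2 |
|---|---|---|
| 6 | 1 | 5 or 6 |
| 7 | 1 | 6 or 7 |
| 8 | 1 | 7 or 8 |

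These counts measure the disagreement between sections. They do not forecast missing data.

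**The case against.** The strongest reply has four parts.

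**The CRF and SAP are not shown.** Section 12.2.4 says how the review is classified. It does not exclude interval fields, and the format of an ECG summary is ordinary SAP detail. A reader might infer that no numeric ECG value exists in the database and that the statistics can never be produced. The documents do not support that: the CRF may hold more than 12.2.4 describes, and sites keep the tracings, so values could be extracted later. What remains is that the protocol commits to parameters and change while describing only a category. A SAP can choose summaries, but it cannot create values that were not recorded.

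**ECG safety does not rest on this table alone.** Clinically significant abnormalities go to the AE page, cardiovascular events are adjudicated separately, and the risk summary in 5.6 names no ECG signal. This stands and lowers the severity. It does not cover group-level shifts below the threshold of clinical significance.

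**Heart rate is well covered.** A reader might infer that a drift in heart rate would also be hidden. It would not, because heart rate is a vital sign.

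**The visit conflict is mild.** Month 12 in 12.2.4 could be read loosely as the label of every annual visit, since that label begins the heading of 9.7.17. A reader might infer that sites will skip the annual ECGs. That assumes they ignore both the schedule table and the visit instructions, which do require them. Even so, the protocol treats Month 12 (9.7.14) and the annual continued follow-up visit (9.7.17) as separate visits, so the literal list in 12.2.4 is incomplete.

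**Conclusion.** The point holds in a limited form. From the data that the protocol says are recorded, the ECG parameter statistics and numeric change from pretreatment in 13.2.3 cannot be computed. Category counts and shifts can. The analytical loss is confined to group-level shifts in PR, QRS and QT/QTc.

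Separately, 12.2.4 disagrees with Table 2 and 9.7.17 on how often ECGs are taken: 1 against 5 to 8 between Screening and EOT/EOS for 6 to 8 years of follow-up. The two defects should not be joined as cause and effect. The three-level recording alone blocks the parameter statistics, and would do so under either visit list.

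The conclusion assumes that the CRF follows 12.2.4 as written; if it already has interval fields, only the protocol text needs correcting. Severity is low. Primary efficacy, power and type I error are unaffected.

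**What to change.** Choose one of two routes, and align the visit list in both cases.

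1. **Record the values.** Add CRF fields in 12.2.4 for the numeric intervals printed on ECGs already being taken (PR, QRS, QT and corrected QT), beside the three-level judgement. Going forward this costs a few fields and a sentence of protocol text. Entering earlier values from retained tracings should be optional: with about 350 subjects at about 170 sites, it is real work.
2. **Change the analysis.** Reword 13.2.3 so that ECGs are summarised as counts and percentages of the three categories by group and visit, with shift tables from Screening to each visit and to the worst post-baseline category. This costs wording only, but accepts that interval shifts below clinical significance will not be examined.

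In either case, align the visit list in 12.2.4 with Table 2 and 9.7.17, so that all three state the same ECG visits. Neither route adds a procedure for subjects.

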12.2.5. Dual Emission X-Ray Absorptiometry

A bone density assessment will be done using the DEXA scan.

12.2.6. Subject Questionnaires

Information about the subject's PBC disease history (ie, date of diagnosis, treatment history, pruritus history, signs and symptoms, and including smoking history) will be collected during Screening. At subsequent study visits (see [Section 7.1.2](#)), subjects will be asked to complete the following questionnaires; they may be asked to initial and date to document confirmation of their responses, and the questionnaires should be filed in the subject's study records. These may require transcription to the CRF by study site staff.

- 5-D Pruritus Questionnaire: This is a questionnaire that has been validated in several different diseases. It assesses symptoms in terms of 5 domains: degree, duration, direction, disability and distribution (Elman 2010).
- Pruritus VAS: A Visual Analogue Scale (VAS) will also be used to assess pruritus in individual subjects.

12.2.7. Laboratory Assessments

Subjects will be instructed to attend each of their study visits (except Screening) in a fasted state, and subjects should remain fasted until their blood samples have been collected. At each visit, the Investigator or designee will verify that the subject has fasted for at least 8 hours and record fasting status in the source and CRF. If the subject reports having eaten (water is permitted) within 8 hours, the Investigator or designee will document accordingly in the source and CRF and remind the subject that fasting is required prior to all study visits.

Blood samples for serum chemistry and hematology will be collected at every visit as detailed in the Schedule of Study Procedures (Section 7.1.2). The number and volume of samples to be collected at each visit will be detailed in the laboratory manual.

Full instructions concerning the number and type of samples to be collected at each visit, the required sample volumes, sample collection methods, sample processing, labeling, and shipping will be provided by the central clinical laboratory in a study specific laboratory manual. All necessary collection supplies will be provided by the central laboratory and will be appropriately assembled for the specific evaluations required at each visit.

All subjects with laboratory tests containing clinically significant abnormal values are to be followed regularly until the values return to normal ranges; until a valid reason, other than investigational product-related AE, is identified; or until further follow up is deemed medically unnecessary.

Laboratory samples will be stored for a maximum of up to 1 year after the end of the study (depending on stability) in the event that retesting is required, and destroyed after 1 year if not analyzed.

The list of laboratory analytes to be tested is shown in Table 10.

Table 10: List of Laboratory Analytes to be Tested

Laboratory Assessment	Analyte
Serum Chemistry	Albumin, blood urea nitrogen (BUN), creatinine, direct bilirubin, total bilirubin, aspartate aminotransferase [AST, SGOT], alanine aminotransferase [ALT, SGPT], ALP, GGT, electrolytes [calcium, chloride, potassium, sodium], glucose, total protein, and blood lipids (total cholesterol, LDL, HDL and very low density lipoprotein [VLDL] fractions and triglycerides [TG]), magnesium, phosphorus, bicarbonate, unconjugated (indirect) bilirubin, conjugated (direct) bilirubin, free fatty acids
Hematology	Hemoglobin, hematocrit, white blood count with differential, neutrophils, lymphocytes, monocytes, eosinophils, basophils, platelets, red blood cell count (including MCV, MCH, MCHC)
Coagulation	Prothrombin time (PT), partial thromboplastin time (PTT), international normalized ratio (INR)
Urinalysis	pH, specific gravity, total protein, glucose, ketones, bilirubin, blood, microscopic exam, urobilinogen, albumin, creatine, leucocytes, nitrates, albumin/creatinine ratio (if positive)
Biomarkers of Hepatic Fibrosis and/or Inflammation	IgM, C-reactive protein (CRP), TNF- α , FGF-19, CK-18, ELF, and others as determined during course of study
Measurement of Liver Fibrosis	Fibroscan
Bone Density Assessment	DEXA
Genetics	DNA including single-nucleotide polymorphisms (SNPs) that may be involved in PBC; RNA
Blood Sample for Future Analysis	PBC autoantibodies and other cytokines and interleukins TBD
Other	OCA (parent and conjugates [glyco and tauro]) and C4

The Investigator should manage subjects with clinically significant lipoprotein abnormalities using local standard of care procedures as appropriate after assessing the individual subject's total cardiovascular risk profile.

Urine-based β -hCG pregnancy tests will be performed in female subjects of childbearing potential per protocol specified visits. If a urine pregnancy test is positive, a serum pregnancy test must be performed to confirm the result. If positive, the Sponsor must be notified and the subject will be followed, as outlined in [Section 12.1.9](#) through pregnancy outcome.

MELD scores, Child-Pugh score, and MRS will be calculated at screening, and at quarterly (MELD and Child-Pugh scores) or semi-annual (MRS) visits based on serum chemistry and coagulation.

13. STATISTICAL METHODS

A statistical analysis plan (SAP), providing details about the specific planned analyses and hypothesis tests, will be prepared and approved by the Sponsor and its designees prior to study database lock, propensity score determination, and unblinding of the double-blind subject treatment assignments.

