Study 747-302 is a clinical outcomes study, supportive of Phase 3 Study 747-301 which was based on a surrogate biochemical endpoint, designed to confirm the clinical benefit of OCA treatment in patients with PBC. A retrospective observational database (Global PBC Study Group [Lammers 2013]) of patients with PBC allowed for a rigorous patient-level meta-analysis and provided an opportunity for a robust assessment of ALP and bilirubin as viable surrogate biochemical parameters and a comprehensive understanding of the natural history of the PBC disease process. Data from the Global PBC Study Group was also utilized to inform the design of the confirmatory outcomes study.

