13.1. Efficacy Analysis

13.1.1. Analysis Populations

The following subject populations will be evaluated and used for presentation and analysis of the data:

- The Randomized Population will include all randomized subjects.
- The Intent-to-Treat (ITT) Population will include all randomized subjects who receive any amount of investigational product (OCA or placebo). The ITT Population will be the primary population used for efficacy analyses. Treatment assignment will be based on the randomized treatment.
- The Safety Population will include all subjects who received any amount of investigational product (placebo or OCA). The Safety Population will be the primary population used for safety analyses. Treatment assignment will be based on the treatment actually received.
- The PK population will include all OCA subjects who have at least one confirmed fasted analyzable sample. Subjects must have been fasting for approximately 8 hours prior to the visit and must not have any major protocol deviations that potentially affect exposure levels. The PK population will be used for OCA PK analyses.
- The Overall Historical Control Population will include subjects from the United Kingdom (UK) -PBC Group and Global PBC Study Group databases with demonstrated comparability to randomized subjects in this clinical study (747-302) with respect to both subject characteristics and disease progression.
- The UK-PBC Historical Control Population will include subjects from the UK-PBC Group databases with demonstrated comparability to randomized subjects in this clinical study (747-302) with respect to both subject characteristics and disease progression.
- The Global PBC Historical Control Population will include subjects from the Global PBC Study Group database with demonstrated comparability to randomized subjects in this clinical study (747-302) with respect to both subject characteristics and disease progression.

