13.1.1.1. Comparability of Historical Controls

Utilization of both historical control/observational databases (UK-PBC and Global PBC Study Group), with more than 6000 subjects each, allow for a rigorous subject level meta-analysis. The historical databases include long-term follow up, detailed subject-level information such as

baseline clinical characteristics, longitudinal liver biochemistry, and long-term outcomes, and span a broad range of subject characteristics that may influence disease (disease state, age, gender, and regional differences in standard of care). Historical controls from both databases will be chosen based on the same study inclusion/exclusion criteria where possible.

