13.1.2.1. Sample Size Re-Estimation Plan

Conducting a long-term outcomes study given the low disease prevalence, relatively slow disease progression, and ethical considerations, which in combination will impact recruitment and event rates, is inherently difficult. As stated in ICH E9, in long-term trials there is an opportunity to check the assumptions that underlay the original design and sample size calculations. The power stated above depends on the total number of events. Thus, the overall survival function can be estimated without unblinding.

Therefore, starting approximately 2 years after the first subject is randomized, the aggregate event rate and sample size based on recruitment and retention will be evaluated in a blinded manner quarterly. This evaluation will determine if any increases in number of subjects are required in order to obtain a total of 121 adjudicated events for the final analysis in the combined groups. Specifically, the pooled number of events will be available during the study in a blinded manner, without any knowledge of the comparative efficacy in the treatment groups. This method for evaluating the sample size does not inflate the type I error rate. Additional subjects may be enrolled as appropriate.

If after 4 years of accruing subjects, despite increases in the number of subjects, it is determined that at least an additional 2 years (ie, total study duration of at least 10 years) are needed to randomize sufficient subjects to achieve a total of 121 adjudicated events, all subjects enrolled from that point forward will receive open-label OCA. Previously randomized subjects will continue to be treated in a blinded manner with either OCA or matching placebo. If this modification is implemented, the alternative primary efficacy analysis is specified in [Section 13.1.9](#).

Any revised sample size or changes to treatment allocation will be justified and documented in a protocol amendment and in the CSR.

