Propensity scores will be estimated using the available covariates that predict receiving the treatment. Only covariates and not outcome variables will be included in the propensity score estimation. Therefore, there is no chance of biasing results in favor of one treatment.

The covariates and factors collected in the historical databases will be specified in the SAP.

Propensity scores will be estimated first through a logistic regression model with treatment group as the dependent variable and the above covariates/factors as independent variables. Then the stratum boundaries are determined based on the propensity score values for both groups (OCA population and control [historical and randomized placebo]) combined or in the OCA population or historical control group alone. Based on recommendations in the literature, quintiles of the estimated propensity score from the combined group will be used to determine the stratum boundary cut-offs for the different strata.

Outcome events collected in the historical database are: death (liver-related and all-cause), liver transplant, hepatocellular carcinoma, and other. Other is defined as cirrhosis or decompensation such as ascites, variceal bleed, and encephalopathy.

The propensity score quintile will be then be used as the stratification factor in the stratified log rank test to compare randomized OCA-treated subjects in the ITT population and historical controls (Overall Historical Control Population: both the UK-PBC Group and Global PBC Study Group databases) on the following outcomes:

- Time to death (all-cause)
- Time to liver-related death
- Time to liver transplant
- Time to liver transplant or death (all-cause)

- Time to liver transplant or liver-related death
- Time to hepatocellular carcinoma

KM estimates of the distribution of the time-to-event will be tabulated and graphed by treatment group. The tabulation will include the KM estimate of the medians and corresponding 95% CIs if the medians can be estimated. The number and percent of subjects censored and with events will be presented. The hazard ratio and 95% CI will be determined based on a Cox regression model stratified by randomization strata to estimate the magnitude of the effect.

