13.1.9. Alternative Primary Analysis

Based on sample size re-estimations, it may be determined that subjects will be enrolled to receive open-label OCA from that point forward, and the new primary efficacy analysis will become the comparison of all subjects in OCA population, to all control subjects (randomized placebo and historical controls) on time to liver transplant or death (all-cause) (see [Section 13.1.2.1](#)). Similar statistical methodology as specified above in [Section 13.1.8](#) for supportive analyses will be utilized.

The propensity score quintile will be then be used as the stratification factor in the stratified log rank test to compare groups. KM estimates of the distribution of the time-to-event will be tabulated and graphed by treatment group. The tabulation will include the KM estimate of the medians and corresponding 95% CIs if the medians can be estimated. The number and percent of subjects censored and with events will be presented. The hazard ratio and 95% CI will be determined based on a Cox regression model stratified by randomization strata to estimate the magnitude of the effect.

In addition, the outcome events specified above in Section 13.1.8 will also be evaluated to compare all subjects in OCA population to all control subjects (randomized placebo and historical controls).

Sensitivity analyses will be conducted limiting to the separate individual historical control databases, ie, UK-PBC Group and Global PBC Study Group. To evaluate the robustness of the propensity score estimations, additional algorithms and factors may be considered.

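### The SAP deadline does not require the control set and propensity covariates for the external-control analyses to be fixed before registry or open-label OCA outcomes can be seen

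*Protocol*

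**What the plan says.** Section 13 sets three limits that the SAP must precede: "prior to study database lock, propensity score determination, and unblinding of the double-blind subject treatment assignments".

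The external-control comparison is described in Sections 13.1.1, 13.1.1.1 and 13.1.8:

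- **Covariates.** "The covariates and factors collected in the historical databases will be specified in the SAP".
- **Eligibility.** "Historical controls from both databases will be chosen based on the same study inclusion/exclusion criteria where possible".
- **Comparability.** Each historical control population consists of registry subjects with "demonstrated comparability to randomized subjects in this clinical study (747-302) with respect to both subject characteristics and disease progression".
- **Safeguard.** "Only covariates and not outcome variables will be included in the propensity score estimation. Therefore, there is no chance of biasing results in favor of" either arm.
- **Already fixed.** A logistic propensity model with treatment group as dependent variable, quintile strata from the combined group, a stratified log rank test and a list of outcomes.

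Section 13.1.1.1 says that the registries already hold long-term outcomes. Section 5.5.1 adds that "Data from the Global PBC Study Group was also utilized to inform the design" of this study.

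Under Section 13.1.2.1, if after 4 years of accrual at least 2 more years are judged necessary (total duration at least 10 years), "all subjects enrolled from that point forward will receive open-label OCA". Section 13.1.9 then makes the primary analysis a comparison of all OCA subjects with randomized placebo plus historical controls on transplant or death. Otherwise the external comparison is supportive only.

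**The concern.** In a randomized double-blind comparison, finalising the SAP before unblinding works because nobody can see results by arm until then. An external-control comparison has no such blind on the control side: the registry outcomes exist. If the open-label switch occurs, part of the OCA side has no blind either.

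The safeguard needed is therefore that the control set and the adjustment covariates are settled before anyone making those choices can see outcomes. A deadline placed at score computation, unblinding or lock does not guarantee that. If the choices were made with outcomes in view, the comparison would lose its claim to be prespecified. This matters most where it can replace the randomized comparison as the primary analysis.

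**Working it through.** **The plan's own figure.** Section 13.1.2 gives 121 events for hazard ratio 0.60, 1:1 allocation, two-sided 5% and 80% power. Schoenfeld's formula gives 4 × (1.960 + 0.842)² / (ln 0.60)² = 31.40 / 0.2609 ≈ 120.4, so 121. It reproduces, but it belongs to the randomized comparison, and this point does not depend on it.

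**What each limit in Section 13 protects.**

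1. *Database lock* comes at the end of the trial. It protects nothing that is visible earlier.
2. *Unblinding of the double-blind assignments* protects the randomized arms. Registry controls and any open-label subjects have no blind to break.
3. *Propensity score determination* is aimed at the external comparison and has force: the covariate list sits in the SAP, so it must be fixed before any score is computed. But a score uses covariates only. Approval before scoring is not approval before outcomes are seen.

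**What can be in view before those limits.**

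- Registry outcomes are already recorded (Section 13.1.1.1).
- Open-label OCA outcomes exist only if the trigger is met. With a switch at year 4 of a 10-year study, 10 − 4 = 6 years of outcomes could accrue with treatment known.
- The disease-progression requirement in Section 13.1.1, read literally, has controls selected partly on their course after baseline. That brings outcome-related information into selection whoever has access to the event data.

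**What remains to be chosen.** The score model, strata, test and endpoint are fixed. Still open are the covariates, the working of the eligibility criteria in registry data (they apply only as far as possible) and the judgement of comparability.

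**The reasoning in Section 13.1.8.** Keeping outcomes out of the logistic model means that the fitted score does not use them. It says nothing about how that model or control set was picked from several candidates, so absence of bias does not follow.

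**Illustration of size (inputs assumed, not in the documents).** Suppose k plausible control or covariate sets differ in log control hazard with standard deviation s, the drug has no effect, and the most favourable is taken. The typical hazard ratio is exp(−E_k × s), where E_k is the expected maximum of k independent standard normals: 0.85, 1.16 and 1.54 for k = 3, 5 and 10.

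| k | s = 0.05 | s = 0.15 |
|---|---|---|
| 3 | exp(−0.0425) = 0.96 | exp(−0.1275) = 0.88 |
| 5 | exp(−0.058) = 0.94 | exp(−0.174) = 0.84 |
| 10 | exp(−0.077) = 0.93 | exp(−0.231) = 0.79 |

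This needs sight of control outcomes only. It treats the whole control group as selectable; under Section 13.1.9 the randomized placebo subjects are also controls and would dilute the shift.

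A second illustration supposes that the treatment comparison itself can be seen for each specification. By simulation (1,000,000 draws, null true, correlation between test statistics from 0.9 down to 0.5), the 2.5% chance of a significant result favouring OCA becomes 5.1% to 9.2% for k = 5 and 6.4% to 14.3% for k = 10. The plan could permit such a view at most for open-label subjects, so these figures overstate the exposure for Section 13.1.8.

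**The case against.** The strongest reply is that Section 13 already protects this analysis. All three limits apply jointly, so the earliest governs. The score model has treatment group as its dependent variable, and for randomized subjects that stays masked until unblinding. In Section 13.1.8 the OCA side is randomized subjects only, so no OCA-versus-registry result can exist before the SAP is approved. That stands. A reader might infer that the deadline is tied to unblinding alone, or that the SAP could always wait until lock; the text supports neither.

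Second, a reader might infer that the people choosing controls have already seen the outcomes. The documents do not say so. Section 5.5.1 reports use of Global PBC data for design; it does not mention UK-PBC there or say who holds subject-level outcomes. Open-label outcomes are conditional on the four-year trigger, and Section 13.1.2.1 requires a protocol amendment for any change in allocation, so the switch could not be silent. It does not, however, require that amendment to fix the control set or covariates.

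Third, the line that "additional algorithms and factors may be considered" might be taken as freedom in the primary analysis. It stands in a paragraph on sensitivity analyses, as a check of robustness, and does not support that reading.

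Fourth, the covariate list and data-access arrangements are proper SAP content, and the SAP is not at hand. That is fair for their content. The latest date by which the SAP must be approved, however, is set in the protocol, and that is what is at issue. An early SAP is allowed but not required.

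**Conclusion.** The point holds in a limited form. Section 13 gives the external-control analyses some protection through the propensity-score limit, but nothing in it puts the choice of controls and covariates ahead of access to outcomes. The disease-progression criterion in Section 13.1.1 weakens the position further, and the assurance in Section 13.1.8 is wrong as reasoned.

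The consequence is modest while the comparison is supportive. It becomes serious if the switch makes it primary. No effect size can be derived from the documents; the hazard ratios of 0.79 to 0.96 and the error rates above rest on assumed numbers of specifications, spreads and correlations. They show what selection could do, not what was done. Actual sight of outcomes by those making the choices is a possibility that the text leaves open, not something it establishes. The change is worth making because it is cheap and protects an analysis that may carry the trial's conclusion.

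**What to change.** In Section 13, add that registry eligibility, index date and propensity covariates for Sections 13.1.8 and 13.1.9 will be approved and dated before registry outcome data are extracted for this analysis, and in any case before the first open-label subject is enrolled. The amendment that Section 13.1.2.1 already requires is a natural place to document this if the switch occurs. Have registry covariates transferred first, and outcomes only after the control set and scores are settled.

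In Section 13.1.1, limit comparability on disease progression to data before the index date. In Section 13.1.8, delete the sentence claiming that there is no chance of bias.

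The cost is writing one SAP section earlier and a two-step data transfer. No sample size, event count or test changes.
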